### 5.2 INCLUSION/ EXCLUSION CRITERIA

If used, the term 'baseline' (BL) within this protocol, unless otherwise specified, is intended to mean, 'pre-study' or 'pre-treatment' (of study medication). It refers to values obtained during the Screening or Day 0 visits, prior to the patient's first dose of study medication. The statistical or calculated definition(s) of 'baseline' to be used in the analyses of the data may be different and will be further defined in the statistical analysis plan (SAP) for this trial.

Patients must meet all of the following criteria to enter the trial.

#### **Inclusion Criteria:**

- (a) Individuals  $\geq$  21 to 65 years old
- (b) Able to provide informed consent & negative urine pregnancy test where appropriate
- (c) Healthy controls must have not consumed any alcohol within 3 months prior to the screening visit
- (d) Healthy controls (non drinkers) must have normal ALT and AST values ( $<45$  U/L)
- (e) Heavy drinkers must have ALT and AST lab values  $<100$  U/L
- (f) Heavy alcohol drinking is defined as  $> 40$  grams per day or 98 grams in a week on average in women and  $> 60$  grams per day or 196 grams in a week on average in men for a minimum of 6 months and within the 3 months prior to study enrolment. Judgment regarding daily and yearly alcohol use will be made by the site investigator.
- (e) Women of child bearing potential should be willing to practice contraception throughout the treatment period

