### Treatment phase,

This investigation will consist of the following 2 study groups:

**Group A:** Healthy non-drinker controls (n = 15)

**Group B:** Heavy drinkers with no known history of liver disease (n=30)

Heavy alcohol drinking will be defined as ongoing consumption > 40 grams per day or >98 grams in a week on average in women and > 60 grams per day or >196 grams in a week on average in men for a minimum of the past 6 months and within the 3 months prior to study enrolment. Judgment regarding daily and yearly alcohol use will be made by the site investigator. During recruiting we will inform the patient that this level of drinking is harmful and will offer referral for treatment. Absence of liver disease will be ascertained according to predefined criteria. Alcohol consumption will be quantified by interview and by a standard alcohol consumption questionnaire.

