**Plasma bile salts are elevated in most patients with alcoholic hepatitis (with or without clinical cholestasis)**. Intrahepatic cholestasis correlates with elevated bile salt levels, Maddrey Discriminant Function, histological severity, and survival. Many patients without histological cholestasis had elevated bile salt levels. There is little information about the effect of heavy alcohol use on bile salt metabolism. Vendemiale and Lieber reported that rats chronically fed a high alcohol diet had increased secretion of bile salts into the bile. Ackehed et al., measured fecal bile salts in 7 patients at admission for detoxification and 9 days later. They found that bile salt excretion was over twice that of normal controls, and slowly declined during abstention. Since the rate of bile salt excretion in steady state must equal bile salt synthesis, this might reflect increased rates of synthesis of bile salts in heavy drinkers, consistent with our hypothesis regarding effects of alcohol on CYP7A1 expression. This elevation in bile salts ought to activate the FXR signaling pathway, with a return of bile salt levels toward normal: the fact that bile salt levels are nearly always increased in AH suggests that this homeostatic system is impaired. As shown in Figure 1, alcohol feeding of mice for 4 weeks reduces levels of Shp. We do not know how alcohol feeding reduced Shp levels. We have previously shown that RXRa protein levels were reduced by alcohol feeding [18]; additional possibilities include direct effects on FXR and reduction in *cis*-retinoic acid, the ligand for RXR^28. We suggest that a primary effect of heavy alcohol use in patients with alcoholic liver disease is inhibition of the ability of FXR to induce Shp. This would result in increased levels of CYP7A1 and sinusoidal bile salt uptake pump, and reduction in the bile salt export pump, resulting in elevated plasma and hepatocyte bile salt levels.

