## 5. PATIENT SELECTION

### 5.1 PATIENT POPULATION

Prospective patients will be identified primarily from the hospitals including Fairbanks Drug and Alcohol Rehabilitation Hospital, outpatient clinics, self-referrals or may be referred by physicians from other hospitals and clinics. Throughout this protocol, the terms 'Principal Investigator (PI)', 'investigator' and 'investigator or designee' are used synonymously. Irrespective of the term used, the intention remains the same: that the overall trial responsibility remains with the PI who has agreed to personally conduct or supervise the trial and who may delegate aspects of the trial conduct, to appropriate, qualified trial site staff who have been informed about their obligations in meeting the above commitments.

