#### **Exclusion Criteria:**

- (a) Active infection as evidenced by positive urine culture, blood culture, or pneumonia, **if necessary, after review of safety labs showing abnormalities, or determination by physical exam performed by PI/sub-I.**
- (b) Serum creatinine  $> 1.5$  mg/dL
- (c) Known co-existing infection with hepatitis C, hepatitis B, or HIV

- (d) Significant systemic or major illness including COPD, CHF and renal failure that in the opinion of the Investigator would preclude the patient from participating in and completing the study.
- (e) Participation in another investigational drug, biologic, or medical device trial within 30 days prior to Screening
- (f) Previous history of jaundice or signs of liver diseases such as spider angioma, ascites, portal hypertension, or history of esophageal varices or hepatic encephalopathy
- (g) Total bilirubin > 2 mg/dl and INR > 1.5
- (h) Women who are pregnant or nursing
  - (i) Presence of any other disease or condition that is interfering with the absorption, distribution, metabolism, or excretion of drugs including bile salt metabolism in the intestine. Patients who have undergone gastric bypass procedures will be excluded (gastric lap band is acceptable).
  - (j) Subjects who are taking warfarin

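### The 3-month abstinence rule can admit former heavy drinkers as healthy non-drinker controls, which can bias the baseline comparison toward the null by an unknown amount

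*Combined protocol and SAP*

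**What the plan says.** Section 5.2 of the protocol, and the synopsis in the same sense, set two criteria specific to controls. Criterion (c) reads "Healthy controls must have not consumed any alcohol within 3 months prior to the screening visit". Criterion (d) begins "Healthy controls (non drinkers) must have normal ALT and AST values" and sets the limit at 45 U/L. Exclusion (f) removes people with "Previous history of jaundice or signs of liver diseases such as spider angioma, ascites, portal hypertension" and related findings. It does not mention past heavy drinking.

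Inclusion criterion (f) defines heavy drinking by gram thresholds held for at least 6 months, and requires that drinking to fall within the 3 months before enrolment.

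On sources, section 5.1 says that prospective patients will be "identified primarily from the hospitals including Fairbanks Drug and Alcohol Rehabilitation Hospital", and goes on to outpatient clinics, self-referrals and physician referrals. It does not say which source supplies which group. On measurement, the synopsis states: "Alcohol consumption will be quantified by interview and by a standard alcohol consumption questionnaire". An alcohol history is taken at screening (Table 1 and section 7.2), but no rule uses it to exclude a control for earlier drinking.

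Section 9.1 compares baseline C4 and FGF19 between 15 controls and 30 heavy drinkers by two-sample t-test, with a stated 83% power at an effect size of 0.95. It adds an ANCOVA adjusting for patient characteristics that it does not list. Section 9.2 lists, as a secondary analysis, a week-4 comparison to see whether treated participants have returned to the control level.

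**The concern.** The two group definitions almost meet. A person with years of heavy drinking who stops goes, at about 3 months, from possible heavy drinker to eligible control, with no wider buffer between the groups. The label of healthy non-drinker then covers both people who have never drunk heavily and people who stopped recently.

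The protocol does not justify 3 months as a washout for the primary endpoints. Its one piece of evidence on bile salts and abstinence, in section 1.1, is a study of faecal excretion in 7 patients at detoxification and 9 days later, where excretion was over twice that of controls "and slowly declined during abstention". That study measured neither C4 nor FGF19 and does not reach 3 months.

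Two analyses are exposed. In 9.1, a residual effect in some controls moves the control mean toward the drinkers and costs power. In the week-4 comparison of 9.2, it moves the reference level toward the drinkers. If treated participants are still on the drinkers' side of normal, recovery then becomes easier to claim.

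**Working it through.** **Inputs from the documents (9.1).** 15 controls, 30 heavy drinkers, effect size d = 0.95 SD, 5% type I error, two-sample t-test, stated power 83%. Sidedness is not stated.

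**Inputs not in the documents (assumptions).**
- k, the number of the 15 controls who are former heavy drinkers: shown for 1, 2 and 3. Their share is f = k/15.
- r, the share of the alcohol effect still present after at least 3 months: shown for 0, 0.25, 0.5 and 1. A residual effect is taken to have the same direction as in current drinkers.

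**Step 1: the plan's figure.** Noncentrality = 0.95 × √(15 × 30 / 45) = 0.95 × 3.162 = 3.004, with 43 degrees of freedom and a two-sided critical value of 2.017. Power is 83.6%, which agrees with the stated 83%. A one-sided test would give 90.5%, so the plan's figure is two-sided.

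**Step 2: dilution.** The expected difference becomes d′ = 0.95 × (1 − f × r). For example, with k = 2 and r = 0.5, d′ = 0.95 × (1 − 0.0667) = 0.887, and the noncentral t gives 78.3%.

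**Step 3: power under dilution.** These are simulated trials with a pooled two-sided t-test and SD 1, in which k controls are shifted by 0.95 × r. The simulation also carries the extra spread that a mixed control group creates.

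| Share of effect persisting (r) | k = 1 | k = 2 | k = 3 |
|---|---|---|---|
| 0 (full reversal) | 84% | 84% | 84% |
| 0.25 | 82% | 81% | 80% |
| 0.5 | 81% | 78% | 75% |
| 1 (no reversal) | 78% | 71% | 63% |

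The noncentral t without the mixture variance is close: 65.2% against 63% at k = 3, r = 1, and nearer elsewhere.

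**Step 4: the margin.** Power is 80% at d′ = 0.906, that is, at f × r = 1 − 0.906/0.95 = 0.046. One former drinker in 15 with the full effect (f × r = 0.067) exceeds this. One with half the effect (0.033) does not.

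**Step 5: shift of the control mean.** This is 0.95 × f × r. It runs from 0.95 × (1/15) × 0.25 = 0.016 SD to 0.95 × (3/15) × 1 = 0.19 SD over the non-zero cells of the table.

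**Step 6: cost of dropping such controls.** With 14, 13 or 12 controls against 30 drinkers and d = 0.95, the noncentral t gives 81.8%, 79.8% or 77.5%.

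**The case against.** A reader might infer that the control group is contaminated through the rehabilitation hospital and that the baseline contrast is therefore diluted. The documents do not support that, for three reasons.

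- **Source.** The rehabilitation hospital is one of several sources and is tied to neither group. It is the natural source of heavy drinkers, and someone admitted for recent drinking would fail criterion (c).
- **Persistence.** What the protocol says about abstinence points toward reversal. Excretion was already falling within days, and section 1.1 also calls alcoholic steatosis reversible. With full reversal nothing is lost. The no-reversal row of the table is a worst case, not an expectation.
- **Scope.** If alcohol has no effect on C4 or FGF19, former drinkers carry none either, so the 9.1 test gains no false positives. The week-4 comparison with controls is labelled secondary. The main analysis in 9.2 compares the randomised arms and does not use controls.

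All of this stands, and it limits the point to what the rule permits.

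It can also be said that dropping such controls gains little. That stands too. If half the effect persists, dropping 1, 2 or 3 gives 82%, 80% or 77–78%, against 81%, 78% or 75% when they stay. If only a quarter persists, keeping them gives at least as much power as dropping them.

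What the objection does not remove is the gap itself. No criterion bars past heavy drinking, and no passage shows normal C4 or FGF19 at 3 months.

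**Conclusion.** The point holds as a gap in the control definition, not as a demonstrated bias. Criterion (c) can admit former heavy drinkers with only 3 months' abstinence. If any are enrolled, and if some of the effect persists, the 9.1 comparison is biased toward the null and the control level used in the secondary week-4 comparison is shifted.

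The size is unknown, because the documents give neither the number of such controls nor the persistence of the effect. Over the assumed range of 1 to 3 in 15, the loss runs from nothing to about 20 percentage points of power, and to about 4 points or less if a quarter of the effect or less remains. Because planned power is only a few points above 80%, a modest combination of the two is enough to take it below that level. The randomised OCA-versus-placebo comparison is unaffected.

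**What to change.** Extend criterion (c) in section 5.2 and in the synopsis with: 'and no past period of at least 6 months of drinking above the gram-per-day thresholds in (f), whenever it ended'. Judge it from the alcohol history already taken at screening.

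Two details of the wording matter. A plain reference to heavy drinking as defined in (f) would exclude nobody new, because (f) requires drinking within the 3 months before enrolment and (c) already rules that out. The daily thresholds (40 g in women, 60 g in men) are used rather than the weekly ones because 98 g and 196 g a week are only 98/7 = 14 g and 196/7 = 28 g a day. A lifetime bar at that level could remove many past moderate drinkers. The price is that people who were above only the weekly limits remain eligible as controls.

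For controls already enrolled, apply the same rule to the recorded history without sight of C4 and FGF19, and repeat the 9.1 comparison without any who fail it. Keep this as a sensitivity analysis beside the planned primary analysis.

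The cost is a short amendment, with no new visit or assay, and it concerns 15 participants who receive no intervention. The downsides are a somewhat smaller control pool, reliance on recalled drinking, and slightly lower power in the sensitivity analysis (82%, 80% or 77–78% after dropping 1, 2 or 3 controls). It is a cheap improvement; the trial's main randomised result does not depend on it.

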#### **Exclusion Criteria:**

- (a) Active infection as evidenced by positive urine culture, blood culture, or pneumonia, **if necessary, after review of safety labs showing abnormalities, or determination by physical exam performed by PI/sub-I.**
- (b) Serum creatinine  $> 1.5$  mg/dL
- (c) Known co-existing infection with hepatitis C, hepatitis B, or HIV

- (d) Significant systemic or major illness including COPD, CHF and renal failure that in the opinion of the Investigator would preclude the patient from participating in and completing the study.
- (e) Participation in another investigational drug, biologic, or medical device trial within 30 days prior to Screening
- (f) Previous history of jaundice or signs of liver diseases such as spider angioma, ascites, portal hypertension, or history of esophageal varices or hepatic encephalopathy
- (g) Total bilirubin > 2 mg/dl and INR > 1.5
- (h) Women who are pregnant or nursing
  - (i) Presence of any other disease or condition that is interfering with the absorption, distribution, metabolism, or excretion of drugs including bile salt metabolism in the intestine. Patients who have undergone gastric bypass procedures will be excluded (gastric lap band is acceptable).
  - (j) Subjects who are taking warfarin

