**Planned Number of Patients**

Approximately 45 subjects [healthy non-drinker controls (n=15) and heavy drinkers (n=30)].

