**Design**

This study consists of two groups of participants – heavy drinking adults (n=30) and non-drinking healthy controls (n=15). There are two components to this study – initial cross-sectional component followed by a 4 week longitudinal component. We are seeking to increase the overall number of subjects allowed to be consented to 150 to ensure that 30 heavy drinking adults can complete this study.

In the cross-sectional component, both groups of participants will undergo testing for bile acid metabolism, markers of gut integrity, oxidative stress, and inflammatory cytokines.

Both groups of participants will participate in the longitudinal component. While healthy controls will not receive any specific intervention, participants in the heavy drinking group will be randomized to receive either OCA (10 mg/day) or placebo for 28 days. At the end of 4 weeks, both groups of participants will again undergo testing for bile acid metabolism, markers of gut integrity, oxidative stress, and inflammatory cytokines.

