### 3.2 SCHEDULE OF STUDY PROCEDURES

**Table 1 Schedule of Study Procedures**

	Screening	D0	D7	D28	D42
Informed Consent	X				
Confirmation of Eligibility Criteria	X	X			
History and physical	X	X		X	
Vitals (Day 42- Heavy Drinker group only)	X	X		X	X
Randomization (Heavy Drinker group only)		X			
Telephone Visit (Heavy Drinker group only)			X		
Alcohol consumption history	X	X		X	
Concomitant medications Assessment (Day7 & 42 -Heavy Drinker group only)	X	X	X	X	X
Adverse Event Assessment (Day7 & 42 -Heavy Drinker group only)		X	X	X	X
Electrocardiogram (Heavy Drinker group only)	X			X	
Dispense Study Medication (Heavy Drinker group only)		X			
Evaluation of study drug compliance (Heavy Drinker group only)			X	X	
CBC with Diff, CMP, PT/ INR Safety labs (Day 28 & 42- Heavy Drinker group only)	X	X		X	X
Urinalysis	X				
Urine Pregnancy test (if applicable)	X	X		X	
Hepatic CYP2E1 measurement study		X		X	
Gut Permeability Test		X		X	
Collection of Research Blood Samples for special investigations 		X		X	
Collection of stool specimen (optional) 		X		X	

Special Investigation Research samples collected for this protocol consist of FGF19, C4, fasting bile acid pool, adipocyte function (fasting NEFA, insulin, adiponectin), oxidative stress (malondialdehyde, 8-isoprostanate), bacterial translocation (plasma LPS, serum sCD14), cytokine measurements (serum TNF- $\alpha$ , IL-1, IL-6 and IL-8) and stool for calprotectin

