#### **Screening Procedures (≤30 days)**

The Screening Visit assessments must be performed within 30 days prior to Day 0 to determine whether the patient meets all the inclusion criteria and none of the exclusion criteria. Patients who do not fulfill all eligibility criteria will not be enrolled in the trial.

Screening Visit procedures are as follows:

- The patient is to review and sign the informed consent document. Informed consent must be obtained from the patient before performing any trial related procedures, including Screening procedures

- Collect medical and disease history
- Collect alcohol use history
- Verify inclusion and exclusion criteria for eligibility
- Perform a physical examination, including height (Screening only) and weight
- Record vital signs
- Perform a standard 12-lead electrocardiogram (ECG) –*Heavy Drinker Group Only*
- Record prior (within 30 days of screening visit) and current concomitant medications.
- Obtain blood samples for serum chemistry and hematology tests
- Obtain urine sample for dipstick urinalysis
- Perform a urine based beta human chorionic gonadotrophin ( $\beta$ -hCG) pregnancy test in females of childbearing potential

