#### **Day 0 Procedures (Randomization and Baseline Study Day)**

- Review inclusion and exclusion criteria for eligibility
- Record vital signs
- Perform a Physical Examination
- Assess and record any pretreatment emergent events
- Record prior (within 30 days of Day 0) and current concomitant medications
- Assess Alcohol Consumption
- Perform an urine pregnancy test in females of childbearing potential
- Perform Hepatic CYP2E1 Measurement Study
- Perform Gut Permeability Test (Lactulose/ Mannitol test)
- Obtain safety labs (CMP, CBC and PT/INR)
- Obtain Research Blood samples as outlined in Table 1: Schedule of Study Procedures
- Obtain Stool Specimen (optional)
- Randomization to study drug (*Heavy drinker group only*)
- Dispense study drug (*Heavy drinker group only*) and instruct patient to begin dosing on the day after Day 0 visit and to take the study medication with water approximately 30 minutes prior to breakfast.

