## **7.4 CLINICAL LABORATORY**

Blood samples for serum chemistry, hematology, and coagulopathy will be collected at every visit as detailed in the Schedule of Trial Procedures (Tables 1). The number and volume of samples to be collected at each visit will be detailed in the Standard Operating Procedures.

Full instructions concerning the number and type of samples to be collected at each visit, the required sample volumes, sample collection methods, sample processing, labeling, and shipping will be provided in a trial specific laboratory manual. All patients with laboratory tests containing clinically significant abnormal values should be followed regularly until the values return to normal ranges, until a valid reason for the AE (other than study medication related AE) is identified, or until further follow up is deemed medically unnecessary.

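### Exclusion (g), read literally, removes only subjects above both the bilirubin and the INR limit; 'or' in place of 'and' would enforce each limit

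*Combined protocol and SAP*

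**What the plan says.** Exclusion (g) reads "Total bilirubin > 2 mg/dl and INR > 1.5". The synopsis and section 5.2 use the same two limits and the same joining word.

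Section 7.2 (Screening Procedures) sets the entry rule: Screening determines whether "the patient meets all the inclusion criteria and none of the exclusion criteria". On Day 0, before randomisation of the heavy drinkers, staff must again "Review inclusion and exclusion criteria for eligibility".

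The protocol describes the blood tests that (g) needs in three places, which do not fully agree:

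- Table 1 (section 3.2) has a row "CBC with Diff, CMP, PT/ INR Safety labs" that is marked at Screening.
- Section 7.4 says "Blood samples for serum chemistry, hematology, and coagulopathy will be collected at every visit".
- The Screening list in section 7.2 says only "Obtain blood samples for serum chemistry and hematology tests" and does not mention PT/INR.

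The synopsis plans "Approximately 45 subjects" (15 controls and 30 heavy drinkers) and asks to raise the "overall number of subjects allowed to be consented to 150" so that 30 heavy drinkers can complete.

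**The concern.** A subject is excluded under (g) only by meeting it, and a condition of the form 'A and B' is met only when A and B are both true. As printed, neither limit works alone: a clearly raised bilirubin with an acceptable INR passes (g), and so does the reverse.

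The wording decides who may enter and, among heavy drinkers, who may be randomised to OCA or placebo. Two members of staff could also read (g) differently and reach opposite decisions on the same subject. Entry matters here because the next safety bloods after Day 0 are at Day 28 (Day 7 is a telephone contact), and the discontinuation reasons in section 5.3 include no bilirubin or INR threshold.

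The point is limited to eligibility. It does not claim a conflict with the description of the heavy-drinker group as having no known liver disease, harm from 10 mg for 28 days, or distortion of C4 or FGF19.

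**Working it through.** **Step 1. What each wording excludes.** The inputs are the two limits in (g): bilirubin 2 mg/dL and INR 1.5. One example is taken for each combination.

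| Bilirubin (mg/dL) | INR | Excluded with 'and' (as printed) | Excluded with 'or' |
|---|---|---|---|
| 1.0 | 1.2 | no | no |
| 4.0 | 1.2 | no | yes |
| 1.0 | 2.0 | no | yes |
| 4.0 | 2.0 | yes | yes |

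The printed wording excludes one combination of four, and 'or' excludes three. The two that differ are those with exactly one raised value.

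**Step 2. Whether another criterion in section 5.2 closes the gap.**

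- Inclusion (d) and the first of the two items lettered (e) cap ALT and AST, at <45 U/L for controls and <100 U/L for heavy drinkers. They do not bound bilirubin or INR.
- Exclusion (b) is a stand-alone creatinine limit.
- Exclusions (d) and (i) concern other illness and conditions that affect drug or bile salt handling. They give no bilirubin or INR value and in practice rest on judgment.
- Exclusion (f) rests on a history of jaundice and on signs or history of liver disease, without a laboratory value.
- Exclusion (j) removes warfarin users, which is one cause of a raised INR.

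None sets a bilirubin or INR limit.

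**Step 3. Why loose drafting is plausible.** In the inclusion list, 'ALT and AST' below a limit enforces each limit, because a subject must satisfy both. The same 'and' in an exclusion has the opposite effect: both values must be out of range before the subject is removed. This suggests a slip but does not prove one.

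**Step 4. How many subjects could be affected.** The documents give no bilirubin or INR distribution. Let *q* be the share of otherwise eligible subjects with exactly one raised value. The values of *q* below are assumptions, applied equally to both groups.

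- Expected number among 45: 45*q*
- Chance of at least one among *n*: 1 − (1 − *q*)^*n*
- Expected extra screen failures under 'or' to enrol 45: 45*q*/(1 − *q*)

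| *q* | Expected among 45 | At least one of 45 | At least one of 30 drinkers | At least one of 15 on OCA | Extra screen failures |
|---|---|---|---|---|---|
| 0% | 0 | 0% | 0% | 0% | 0 |
| 1% | 0.45 | 36% | 26% | 14% | 0.45 |
| 2% | 0.90 | 60% | 45% | 26% | 0.92 |
| 5% | 2.25 | 90% | 79% | 54% | 2.37 |

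For example, at *q* = 2%: 45 × 0.02 = 0.90; 1 − 0.98^45 = 0.597; 45 × 0.02/0.98 = 0.92.

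**Step 5. Room under the consent ceiling.** 150 − 45 = 105 consents above the planned number. These must also cover all other screen failures and replacements for dropouts, and the documents do not say how many are already used.

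**The case against.** The strongest reply is that no consequence is shown. Staff may already read (g) as a list of two separate exclusions, in which case changing the word alters nobody's eligibility. If a joint threshold was intended, 'or' tightens a deliberate choice and could turn away people with isolated benign hyperbilirubinaemia, in a trial that needed a higher consent ceiling. Other safeguards also narrow the gap: the open-ended list of liver signs in (f), physical examination at Screening and Day 0, the ALT/AST caps and the warfarin exclusion. Every non-zero patient count rests on an assumed *q*.

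Much of this stands. Intent is not documented, the number affected may be zero, and the 105 consents are not free slack. It does not rescue the wording. If 'or' was meant, the text should say so; if 'and' was meant, nothing in the protocol states or explains a joint threshold. The other safeguards depend on history, signs or judgment, or measure something else, so they do not replace a numeric limit. The PT/INR omission from the Screening list is editorial, since Table 1 and section 7.4 both provide for the test. It is still worth aligning, because (g) cannot be applied without an INR.

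**Conclusion.** The concern holds. Applied as written, (g) admits subjects with one raised value that no other criterion limits. It covers one of four combinations, where 'or' would cover three. That part follows from the text alone and needs no assumption.

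The number of subjects involved is unknown. It is nil if *q* is zero; at an assumed *q* of 1% to 5%, about 0.5 to 2.3 of the 45 would be expected. The weight is that of a cheap improvement that should be made. Power and the planned analyses are unaffected.

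**What to change.** - In the synopsis and in section 5.2, change (g) to: total bilirubin > 2 mg/dL *or* INR > 1.5. If a joint condition was intended, say so explicitly and give the reason.
- Add PT/INR to the Screening list in section 7.2 so that it matches Table 1 and section 7.4.
- If anyone above only one of the limits is already enrolled, list them by group and arm and keep them in the primary analysis.

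The cost is one word in two places and one added item in a list. CMP and PT/INR are already scheduled at Screening, so no test is added. The downside is possibly a few more screen failures, 0 to about 2.4 expected over the assumed range, some of which might be benign isolated bilirubin elevations.
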